8.3.8 Unscheduled visit

Unscheduled visits may be performed at any time during the study. Depending on the reason for the unscheduled visit (e.g., AE), appropriate assessments will be performed based on the judgment of the investigator, and the AEs will be recorded in the eCRF. After an unscheduled visit, the regular scheduled study visits must continue according to the planned visit and assessment schedule as originally planned.

8.4 Methods of Data Collection

Data will be entered by the center's study nurses. The data entered in the CRFs will be checked by the clinical monitor for data quality and integrity. All data will be entered into one database and signed by the principal investigator or study physician. Data management will perform data cleaning (e.g. range checks), pose queries and prepare the data for data analysis.

8.4.1 Efficacy Parameters

The primary efficacy variable is the change in pulmonary vascular resistance from baseline to week 24.

Secondary efficacy endpoints will be tested hierarchically:

EudraCT: 2021-001633-40	Version 1.7 15.01.2025	ESRA
-------------------------	---------------------------	------

- change of cardiac index at rest (baseline to 24 weeks)
- change of total pulmonary resistance (baseline to 24 weeks)
- change of diffusion capacity of the lung (baseline to 24 weeks)
- change of 6-minute walking distance (baseline to 24 weeks)
- change of WHO functional class (baseline to 24 weeks)
- change in QoL (SF-36, physical summation score; baseline to 24 weeks)

Exploratory endpoints

The following parameters will be assessed in every patient according to the visits schedule and analyzed as **exploratory variables**. Exploratory endpoints will be analyzed as change from baseline to 12 and to 24 weeks as available according to assessment schedule.

QoL assessed by the SF-36 questionnaire

- mental summation score as well as the 8 sub scores

WHO functional class

Echocardiography

- systolic pulmonary arterial pressure (sPAP, mmHg), right ventricular area (RV-area, cm²), and right atrial area (RA-area, cm²), tricuspid annular plane systolic excursion (TAPSE), left ventricular eccentricity index (LV-EI), RV-pump function and LV-pump function (LV-EF, %).

Lung function

- FEV1 (forced expiratory volume in 1 second), TLC (total lung capacity), DLCO (diffusing capacity of the lung)

Analyses of blood samples

Venous blood will be analyzed to determine:

- NT-pro BNP

Blood for blood gas analyses

- oxygen partial pressure, carbon dioxide partial pressure, oxygen saturation of the blood (SpO₂), pH values, bicarbonates, base excess

Pulmonary hemodynamics by right heart catheterization

- sPAP, mPAP, diastolic pulmonary artery pressure (dPAP), pulmonary artery wedge pressure (PAWP), right atrial pressure (RAP), cardiac output and ejection fraction (CO), central venous saturation, via blood gas analysis from pulmonary artery (SvO₂)

EudraCT: 2021-001633-40	Version 1.7 15.01.2025	ESRA
-------------------------	---------------------------	------

8.4.2 Safety Parameters

Safety variables include and will be determined:

1. Electrocardiogram (ECG)
2. Vital signs: Blood pressure, heart rate/pulse, oxygen saturation
3. Hemodynamics: Cardiac Output, SvO₂ (during RHC)
4. Echocardiography
5. Clinical laboratory investigations
6. Concomitant medication
7. Concomitant diseases
8. Adverse events

Clinical worsening will be defined as time to first event out of:

- worsening of WHO functional class
- deterioration of 6MWD >15% compared to baseline
- need of initiation of targeted PAH treatment
- hospitalization due to worsening of right heart function
- all cause death or lung-transplantation
- atrial septostomy

Safety variables

Laboratory, electrocardiogram, vital signs, assessment of adverse events and serious adverse events will serve as safety parameters.

Patients with a serious adverse event occurring during the study treatment will be followed by the study team until the serious adverse event will have resolved to the pre-study level and/or will have been addressed according to best clinical practice. Patients withdrawing from the study prematurely will have a final examination.

If a patient withdraws from study treatment and agrees to stay in the study, study related examinations will be performed and data will be obtained according to protocol.

8.5 End of Trial

The trial will end once the last patient has had their safety follow-up visit by phone 30 ± 14 days after last intake of study drug.

8.6 Plan for Treatment of Care after the Trial

Riociguat (MK-4836) is not approved for the indications studied and therefore cannot be further prescribed after the end of the study. In case of development of manifest PAH, measured by RHC

EudraCT: 2021-001633-40	Version 1.7 15.01.2025	ESRA
-------------------------	---------------------------	------

during Visit 3, a targeted PAH therapy will be initiated according to the guidelines. Otherwise the study medication will be discontinued. Patients will be offered a follow-up for 6 more months in terms of early detection any clinical deterioration.

9 Adverse Events

9.1 Definitions

9.1.1 Adverse Event

An AE is any unfavorable and unintentional change in the body temporally associated with the use of a drug whether or not considered related to the use of the product. A clinically significant worsening of a pre-existing condition is also assumed to be an adverse event. AEs may also occur subsequent to overdose, improper use, or due to premature withdrawal of a product.

An AE may be:

- New symptoms/ medical conditions
- New diagnosis
- Significant changes of laboratory parameters
- Intercurrent diseases and accidents
- Worsening (change in nature, severity or frequency) of medical conditions/ diseases existing before clinical trial start
- Recurrence of disease
- Increase of frequency or intensity of episodical diseases.
- Events related or possibly related to concomitant medications

A pre-existing disease or symptom will not be considered an adverse event unless there will be an untoward change in its intensity, frequency or quality. This change will be documented by an investigator.

Surgical procedures themselves are not AEs; they are therapeutic measures for conditions that require surgery. The condition for which the surgery is required may be an AE. Planned surgical measures permitted by the clinical trial protocol and the condition(s) leading to these measures are not AEs, if the condition leading to the measure was present prior to inclusion into the trial.

AEs are classified as "non-serious" or "serious".

All AEs need to be documented in data entry forms and sent to the sponsor.

9.1.2 Serious Adverse Event

A serious adverse event (SAE) is one that at any dose:

- Results in death

EudraCT: 2021-001633-40	Version 1.7 15.01.2025	ESRA
-------------------------	---------------------------	------

- Is life-threatening (the term life-threatening refers to an event in which the subject was at risk of death at the time of event and not to an event which hypothetically might have caused death if it was more severe)
- Requires subject hospitalization or prolongation of existing hospitalization (unless the admission results in a stay of less than 12 hours or the admission is pre-planned or the admission is not associated with an adverse event)
- Results in persistent or significant disability/ incapacity or is a congenital anomaly/ birth defect.
- Is another important medical event which may not fulfil the aforementioned criteria but may jeopardize the patient based upon appropriate medical judgment. Medical and scientific judgment should be exercised in deciding whether expedited reporting is appropriate in other situations. These should also usually be considered serious (e.g. treatment at home for allergic bronchospasm).

The following events don't need to be reported as an SAE:

- Planned hospitalization due to scheduled elective catheterization (e.g. scheduled re-evaluation of pulmonary disease), scheduled hospitalization for further diagnostics or therapeutic measures.

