9.2 Period of Observation and Documentation

All AEs reported by the subject or detected by the investigator, will be collected during the trial and must be documented on the appropriate pages of the CRF. AEs must also be documented in the subject's medical records.

In this trial, all AEs that occur after first administration of the IMP up to the last visit (i.e. follow-up visit) will be documented on the pages provided in the CRF. AEs will be assessed by the investigator using no-leading questions or observed during any visit during the whole study. The patient should be motivated to report any AEs by phone to the investigator occurring in between study visits. All subjects who have AEs, whether considered associated with the use of the trial medication or not, must be monitored to determine the outcome. The clinical course of the AE will be followed up until resolution or normalization of changed laboratory parameters or until it has changed to a stable condition.

Each event should be described in detail along with start and stop dates, severity, relationship to investigational product, action taken and outcome.

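### The SAE carve-outs for scheduled and pre-planned admissions have no date or pre-existing-condition test, so an event serious only through an admission booked on treatment can lose SAE status

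*Protocol*

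**What the plan says.** Protocol 9.1.2 takes hospital admissions out of SAE status in two places.

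- **Inside the hospitalisation criterion.** An admission does not count if the stay is under 12 hours, or if "the admission is pre-planned or the admission is not associated with an adverse event".
- **In a separate list after the criteria.** Under the lead-in "The following events don't need to be reported as an SAE", the protocol names planned admission for elective catheterisation and then, without further condition, "scheduled hospitalization for further diagnostics or therapeutic measures".

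Protocol 9.1.1 contains a pre-existing-condition test, but for a different purpose. Planned surgery allowed by the protocol, and the condition behind it, are not adverse events "if the condition leading to the measure was present prior to inclusion into the trial".

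SAE status then controls several outputs: the 24-hour report (Protocol 9.3 and 9.4), SUSAR classification (Protocol 9.1.4) and the SAE tables (Protocol 10.3.1; SAP 5.4, 7.6.2.1 and Table 3 of the appendix).

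**The concern.** An exemption for planned admissions is meant to keep out admissions that have nothing to do with what happens on study drug. That works only if the text fixes when the admission was planned and requires that its cause was present beforehand and has not worsened. Section 9.1.2 does neither. An admission arranged because of an event on treatment is scheduled, and is for diagnostics or therapy, so it meets the wording of the exemption.

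Safety and tolerability in this population is a stated secondary objective, and the SAE table is one of only three planned adverse-event tables. A rule that makes seriousness depend on whether an admission was booked or unbooked, rather than on why it happened, can misclassify events in that table and delay or prevent expedited assessment.

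**Working it through.** The plan gives no figure to reproduce. The check compares the provisions and then traces where an affected event could still appear.

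**Step 1. What each provision tests.**

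| Provision | Decides | Planning date required? | Condition must pre-date trial? | Must not have worsened? |
|---|---|---|---|---|
| 9.1.1, planned surgery | whether there is an AE | no | yes | not in that sentence, but the section treats worsening of an existing condition as an AE |
| 9.1.2, hospitalisation criterion | whether an admission makes an AE serious | planned in advance, but of no stated date | no | no |
| 9.1.2, exemption list | whether an SAE report is needed | scheduled, but by no stated date | no | no |

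**Step 2. Does the hospitalisation criterion close the gap?** No. Its exceptions are joined by 'or'. Lack of association with an adverse event is one route out and prior planning is another. A pre-planned admission is therefore excluded even when an adverse event caused it.

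**Step 3. A worked case (illustration, not trial data).** An event starts in week 9. In week 10 an in-hospital work-up is booked for a later date. No other seriousness criterion is met. The admission is scheduled and diagnostic, so under 9.1.2 no SAE report is needed. The 24-hour report and SUSAR classification both start from an SAE, so neither is triggered.

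**Step 4. Where could that event still be tabulated?** SAP 7.6.2.1 and appendix Table 3 plan three tables.

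1. *SAEs*: absent, because SAE status is lost.
2. *Drug-related AEs*: present only if causality is definite, probable or possible (Protocol 9.1.6). An event rated not assessable counts as suspected for SUSAR purposes (9.1.4) but is not drug-related under 9.1.6, so it could miss both.
3. *AEs by frequency*: the cut-off is 5% (at least 5% in 7.6.2.1, more than 5% in Table 3). The SAP does not say whether the base is all patients or each arm.
   - All patients: 1/35 = 2.9%, below the cut-off. Two patients with the same event give 2/35 = 5.7%, above it.
   - Per arm: arm sizes are not given. Assuming 17 and 18, 1/17 = 5.9% and 1/18 = 5.6%, both above it. In general 1/n exceeds 5% when n is below 1/0.05 = 20.

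With the cut-off applied to all 35, a single event not judged drug-related could thus be in none of the three tables. With the cut-off applied per arm at the assumed sizes it would appear, but as a non-serious event.

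**The case against.** The strongest reply is that little is lost. Protocol 9.2 says "All AEs reported by the subject or detected by the investigator, will be collected during the trial", so the event is recorded and followed. Death, life threat and disability still make it serious, as does the judgement-based criterion: "Is another important medical event which may not fulfil the aforementioned criteria but may jeopardize the patient based upon appropriate medical judgment". Unscheduled admissions are not covered by the exemption list. Related events reach the drug-related table whatever their seriousness. The protocol synopsis also says all data will be listed. For progression of the lung disease, Protocol 6.5.1 foresees prompt introduction of therapy, so a slow elective admission is not the expected path there. Many investigators would also read pre-planned as planned before the trial.

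Most of this stands, and it limits the point to seriousness that rests on hospitalisation alone. It does not remove the point. The important-event criterion asks for individual judgement where a definition should decide. The conventional reading of pre-planned is not written down, and the exemption list asks only that the admission be scheduled.

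Three stronger readings are tempting but not supported:

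- **That 9.1.1 and 9.1.2 contradict each other.** They answer different questions: whether something is an adverse event, and whether an admission makes it serious. Nor does 9.1.1 already hold the full remedy, since it asks about the condition and not about when the admission was planned.
- **That disagreement between the SAE table and clinical worsening would show an error.** The composite includes functional-class and walking-distance components that need not be SAEs. Its only admission component is "hospitalization due to worsening of right heart function". The two outputs measure different things by design.
- **That the event vanishes from the trial record.** It stays an adverse event.

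**Conclusion.** The gap is real and lies in a stated rule, not merely in missing detail. Both carve-outs in Protocol 9.1.2 literally exempt an admission booked because of an on-treatment event. What can be lost is SAE status for an event that is serious through that admission alone, together with the reporting and tabulation that follow from it.

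The size cannot be given. The documents do not show that any such admission occurred, and they give no arm sizes. A reader might take 5.6 to 5.9 percentage points per missed patient as the effect. That is only one divided by an assumed arm of 18 or 17, and it presumes a patient with no other SAE. The firmer statement is conditional: with the 5% cut-off applied to all 35 patients, one event not judged drug-related could be in no planned adverse-event table. The safety tables are descriptive, and the primary analysis is unaffected.

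**What to change.** **Protocol 9.1.2.** Limit both carve-outs, the pre-planned clause in the hospitalisation criterion and the exemption list, to:

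- admissions for protocol-required catheterisation; and
- admissions planned before informed consent for a condition that was present before inclusion and has not worsened since. This adds a planning date and an explicit no-worsening condition to the test in 9.1.1.

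State that an admission arranged because of a new or worsened event is not exempt. Amending only the exemption list would leave the pre-planned clause open.

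**SAP 7.6.2.1.** Enrolment has ended at 35 (SAP section 8), so new protocol wording may no longer change what was reported. Apply the rule in the analysis instead. Before unblinding or database lock, check adverse events after first dose for associated admissions and reclassify where needed. Use medical records where the CRF does not record the admission: the documents name hospitalisation on the SAE form (9.3, 9.4), but the countermeasure categories for adverse events (9.1.6) do not name it, and no general admissions field is described.

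**If lock has passed** (its status is not stated), disclose the exemption in the report and list the exempted admissions.

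**Cost.** Modest source checking for 35 patients and possibly a few more SAEs. No sample size, power or alpha figure changes.

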9.1.3 Expectedness

An ‘unexpected’ adverse event is one the nature or severity of which is not consistent with the applicable “Summary of Product Characteristics” (SmPC) or scientific literature. Furthermore, reports which add significant information on specificity or severity of a known adverse reaction constitute ‘unexpected’ events.

9.1.4 Suspected Unexpected Serious Adverse Reaction (SUSAR)

SAEs that are both suspected, i.e. possibly related to IMP and ‘unexpected’, i.e. the nature and/ or severity of which is not consistent with the applicable product information are to be classified as Suspected Unexpected Serious Adverse Reactions (SUSARs). The definition covers also medication errors and uses outside what is foreseen in the protocol, including misuse and abuse of the product.

In case, either the investigator who primarily reported the SAE or the second assessor classify the SAE as ‘suspected’ (i.e. either *related* or *probably* or *possibly related* to the IMP or *not assessable*) and the SAE is unexpected it will be categorized as a SUSAR.

EudraCT: 2021-001633-40	Version 1.7 15.01.2025	ESRA
-------------------------	---------------------------	------

All SUSARs are subject to an expedited reporting to the responsible IRB / EC and to all participating investigators.

9.1.5 Grading of AEs

The **grading** of an AE should be assessed by the investigator according to the 5-grade scale as follows:

- Grade 1: mild AE, temporary event which is tolerated well by the subject
- Grade 2: moderate AE; event which results in discomfort for the subject and impairs his/ her normal activity
- Grade 3: severe AE; event which results in substantial impairment of normal activities of subject
- Grade 4: life-threatening AE or AE causing disablement
- Grade 5: death related to AE

9.1.6 Relationship and outcome of AEs, action taken

Causality assessment of an AE/SAE regarding an investigational product (causality) is determined and documented by the investigator based on the following criteria:

- definite: There is a definite relationship.
- probable: An AE that has a reasonable possibility that the event is likely to have been caused by IMP. The AE has a **timely relationship** and **follows a known pattern of response**, but a potential alternative cause may be present.
- possible: An AE that has a reasonable possibility that the event may have been caused by IMP. The AE has a **timely relationship** to the IMP; **however, the pattern of response is untypical**, and an alternative cause seems more likely, or there is significant uncertainty about the cause of the event.
- unlikely: Only a remote connection exists between the IMP and the reported adverse event. Other conditions including concurrent illness, progression or expression of the disease state or reaction of the concomitant medication appear to explain the reported adverse event.
- Definitely not: No relationship. An AE that does not follow a reasonable temporal sequence related to IMP and is likely to have been produced by the subject's clinical state, other modes of therapy or other known etiology.
- not assessable: There is insufficient or incomplete evidence to make a clinical judgement of the causal relationship.

An AE/SAE will be classified as drug-related if the relationship determined by the investigator is possible, probable, or definite (causal relationship).

The **outcome** of an AE at the time of the last observation will be classified as:

Recovered/ resolved	all signs and symptoms of an AE disappeared without any sequels at the time of the last interrogation
Recovering/ resolving	the intensity of signs and symptoms has been diminishing and/ or their clinical pattern has been changing up to the time of the last interrogation in a way typical for its resolution
Not recovered/ not resolved	signs and symptoms of an AE are mostly unchanged at the time of the last interrogation
Recovered/ resolved with sequel	actual signs and symptoms of an AE disappeared but there are sequels related to the AE
Fatal	resulting in death. If there is more than one adverse event only the adverse event leading to death (possibly related) will be characterized as 'fatal'
Unknown	the outcome is unknown or implausible and the information cannot be supplemented or verified

The **action taken** with the IMP will be assigned to one of the following categories:

'Dose not changed': no change in the dose of IMP.

'Dose reduced': reduction in the dose of IMP.

'Dose increased': increase in the dose of IMP.

'Drug withdrawn': discontinuation of IMP.

'Unknown': the information is unknown or implausible and it cannot be supplemented or verified.

'Not applicable': the question is implausible (e.g. the subject is dead).

The term 'Countermeasures' refers to the specific actions taken to treat or alleviate adverse events or to avoid their sequels. The following categories will be used to categorize the countermeasures to adverse events:

None: no action taken

Drug treatment: newly-prescribed medication or change in dose of a medication

EudraCT: 2021-001633-40	Version 1.7 15.01.2025	ESRA
-------------------------	---------------------------	------

Others: other countermeasures, e.g. an operative procedure

9.2 Period of Observation and Documentation

All AEs reported by the subject or detected by the investigator, will be collected during the trial and must be documented on the appropriate pages of the CRF. AEs must also be documented in the subject's medical records.

In this trial, all AEs that occur after first administration of the IMP up to the last visit (i.e. follow-up visit) will be documented on the pages provided in the CRF. AEs will be assessed by the investigator using no-leading questions or observed during any visit during the whole study. The patient should be motivated to report any AEs by phone to the investigator occurring in between study visits. All subjects who have AEs, whether considered associated with the use of the trial medication or not, must be monitored to determine the outcome. The clinical course of the AE will be followed up until resolution or normalization of changed laboratory parameters or until it has changed to a stable condition.

Each event should be described in detail along with start and stop dates, severity, relationship to investigational product, action taken and outcome.

